2.14 Adverse Event Recording

All data captured must be supported by the Investigator's timely assessment and documentation of the adverse event in the case report forms or source documents. All documented adverse events will be reviewed by the Sponsor or designee to determine whether the adverse event meets regulatory reporting requirements and to ensure timely adverse event reporting to meet local and global regulatory requirements.

Adverse Events Pertaining to the TempSure Device:

Mild discomfort during treatment may be experienced by the subject. Typically, the discomfort is temporary and localized within the treatment area. Mild edema (swelling) and erythema (redness) may occur. Initial studies indicate that these side effects typically resolve within 2 to 24 hours.

Other anticipated side effects may include; pain, skin burns, bleeding, scarring, crusting, bruising, infection, itching,

prolonged edema (swelling) and erythema (redness), hardness, and nodules. Loss of hair pigment may also occur within and adjacent to the treatment area.

Adverse Events Pertaining to Gel:

The gel is a water-based gel that may be placed on the skin during the TempSure® Firm treatment. No known adverse events are documented. However, an allergic reaction is always possible when placing a topical gel onto the skin. Allergic reaction may include a mild reaction such as skin redness, irritation, or hives.

Adverse Events Pertaining to Neutral Pad:

Mild heat or hot spots may be felt during treatment by the subject. If the subject reports heat at the pad site, evaluate the site, check for epidermal injury. Skins burns may occur if subject does not report if the pad becomes too hot.

Adverse Events Pertaining to the Surgical Marker:

Using surgical marker has minimal risks and may produce effects on the body such as redness or a rash. Markings may remain visible for a few days or may be removed with alcohol.

Other Cautions:

Incomplete response or no response may occur since some subjects may not respond to treatment. After the subject has completed their participation in the study, a treatment on the untreated flank using the TempSure® Firm may be performed upon the subject's request at no cost.

2.15 Statistical Analysis

2.15.1 Hypothesis

For this study to be considered a success, the following criteria must be met:

1. Correct identification of pre-treatment images when compared to post treatment (12 week) images will be $\geq 80\%$.
2. Caliper measurements show statistically significant improvement on treatment area versus control.
3. The subject satisfaction rates at 12-week follow up visit will be $\geq 80\%$.
4. The side effect profile is acceptable to the Physician as it relates to this type of treatment.

2.15.2 Sample Size Rationale

The primary outcome will be the change in the subjective assessment of the reduction in fat as assessed by blinded evaluation of photographs taken before and after treatments. The primary endpoint will be defined as the 12-week follow up post final treatment with an objective of 80% correct evaluation. The sample size was determined based on a two-sample t-test with a two-sided significance level of 0.05 and power of 95%. A hypothetical control group would assumedly result in correct identification of follow up pictures 50% of the time, with a standard deviation of 50% resulting from an equal amount of correct and incorrect answers. Our objective of 80% correct average evaluation of post treatment photos with a conservative 20% expected standard deviation. Based on these assumptions it was determined that a total of at least 43 patients would be required for the study to have a successful primary outcome.

One of the secondary outcomes will be the change in fat layer thickness as assessed by caliper measurements before and after treatments. Previous studies have shown a change in caliper measurements of 7.0mm in a treated flank, and 0.7mm change in the control. The maximum standard deviation seen for any measurements (treated or control, baseline or follow up) was 5.8 which is used as an assumed standard deviation for sample size calculations.^v Assuming 0.05 significance level and adjusting for a power of 95%, it was determined that 14 subjects would be needed to have a successful secondary outcome measure.

Another secondary outcome is the subject satisfaction rate. The sample size is calculated similarly to the primary outcome and yields the same results.

Based on these assumptions it was determined that a total of 43 patients would be required for the study, which was the maximum calculated among all the study outcome measures. To allow for minor departures in these assumptions and to account of potential subject dropout it was decided to enroll 68 subjects.

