2.15.5 Analysis of Efficacy Variables

The primary efficacy variable is blinded evaluation of photographs from baseline to Visit 8 (12-week follow up) with respect to fat reduction. Baseline is defined as the last assessment prior to the first treatment. Photos will be graded and the total and percentage of photos correctly identified will be compiled and analyzed. Correct identification percentages will be calculated for each individual reviewer as well as a summary for all three reviewers. Clinical success of grading will be declared if 80% independent reviewers achieve 80% correct identification of the photos.

The secondary efficacy variables are caliper measurements of fat thickness and subject satisfaction rates. As with the primary efficacy variable the assessment at Visit 8 (12-week follow up) will be primary. The analysis and summaries for caliper measurements will include a pairwise treatment group comparison as well as repeated measure ANOVA analysis. Statistical significance with respect to both the treatment and control group comparisons as well as repeated measures of the treatment group will be declared if the two-sided p-value is <0.05 . For each treatment group and timepoint of the caliper measurements a statistical summary will be completed. The summary will include sample size mean, median, standard deviation, minimum, and maximum. The statistical significance of the mean change from baseline to follow-up for each group as well between the treatment and control will be determined using a paired t-test. Subject satisfaction will be analyzed with standard descriptive statistics which include total number of responses in each category as well as the percentage of responses for each category. Clinical success of subject satisfaction surveys will be declared if at least 80% of subjects respond they are satisfied.

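### The 95% power belongs to a t-test the plan never runs; under the plan's own 80% success rule, a true rate of 80% gives only about a 50% chance of primary success

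*Combined protocol and SAP*

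**What the plan says.** **Sizing (2.15.2, Sample Size Rationale).** The plan states that "The sample size was determined based on a two-sample t-test with a two-sided significance level of 0.05 and power of 95" percent. The comparator is not enrolled: "A hypothetical control group would assumedly result in correct identification of follow up pictures 50% of the time". Its SD is put at 50%. The treated side is entered as "Our objective of 80% correct average evaluation of post treatment photos with a conservative 20% expected standard deviation". From these inputs the plan concludes that "a total of at least 43 patients would be required for the study to have a successful primary outcome". Subject satisfaction is said to be sized in the same way with the same result. Enrolment is then set at 68 to allow for dropout and for departures from the assumptions; no dropout rate is given.

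**Success rule (2.15.1, Hypothesis).** "For this study to be considered a success, the following criteria must be met". The first criterion is that "Correct identification of pre-treatment images when compared to post treatment (12 week) images will be" at least 80%. The third is a satisfaction rate of at least 80% at 12 weeks.

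**Analysis (2.15.5, Analysis of Efficacy Variables).** Correct identifications are counted and expressed as percentages, per reviewer and over all three. "Clinical success of grading will be declared if 80% independent reviewers achieve 80% correct identification of the photos". Satisfaction is summarised descriptively and judged against 80%. Neither outcome has a hypothesis test or a confidence interval. The t-tests in the plan are for demographic and medical history variables (2.15.4) and caliper measurements (2.15.5).

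**The concern.** Power describes a particular decision rule. The rule powered in 2.15.2 is rejection of equality between two group means, one of them imaginary. The rule that decides the trial is whether a point estimate reaches 80%. The two coincide only by accident, and here they are far apart, because the treated mean used for planning is itself the pass mark. An estimate centred on its own threshold falls on either side about equally often, and more subjects narrow its spread without moving its centre.

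If the device performs exactly as the calculation supposes, the trial misses its primary criterion about half the time, while the protocol tells sites, the IRB and the sponsor that 43 patients suffice at 95% power. All the criteria in 2.15.1 must be met, so the same flaw in the satisfaction criterion lowers the chance of overall success further.

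**Working it through.** **Step 1. Reproduce the plan's 43.** Inputs from 2.15.2: difference 0.80 − 0.50 = 0.30; SDs 0.50 and 0.20; two-sided alpha 0.05; power 95%.

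- Normal approximation: n per group = (0.50² + 0.20²)(1.960 + 1.645)² / 0.30² = 0.29 × 12.995 / 0.09 = 41.9, so 42.
- Noncentral t at n = 43 per group: standard error = √(0.29/43) = 0.0821; noncentrality = 0.30/0.0821 = 3.65; 84 degrees of freedom. Power is 95.1% at 43 and 94.6% at 42.

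So 43 is right as the number **per group** for that t-test, the second group of 43 being hypothetical. The arithmetic of the 43 is sound; the question is whether the power carries over to the rule in use.

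**Step 2. Chance of meeting the overall 80% rule when the true rate is 80%.** With one reading per subject (equivalently, three reviewers who always agree), X ~ Binomial(n, 0.80), and success means X ≥ the smallest whole number not below 0.8n.

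| Subjects | Correct needed | Chance of success |
|---|---|---|
| 43 | 35 | 50.0% |
| 55 | 44 | 58.0% |
| 68 | 55 | 50.0% |

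The 58% at 55 is discreteness: 44/55 is exactly 80%, whereas 35/43 is 81.4% and 55/68 is 80.9%.

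Pooling three fully independent reviewers gives 3n readings: 104 of 129 needed with 43 subjects (48.2%) and 164 of 204 with 68 (48.6%). Simulated intermediate agreement stays between about 48% and 51%.

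**Step 3. The reviewer-level rule in 2.15.5.** Eighty percent of three reviewers is 0.8 × 3 = 2.4, so read literally all three must reach 80%. With 43 or 68 subjects:

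- Independent reviewers: 0.500³ = 12.5%.
- Assumed correlation 0.5: about 25%.
- Assumed correlation 0.95: about 44%.
- Full agreement: 50%.

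The documents give no inter-reviewer agreement, so 12.5% to 50% is an assumption range. On this reading 50% is the best case.

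**Step 4. True rate needed for a 95% chance under the overall rule** (binomial tail solved for the rate).

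| Subjects | Independent reviewers, pooled | Full agreement |
|---|---|---|
| 43 | 85.5% | 88.6% |
| 68 | 84.4% | 87.1% |

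Using the plan's own SD of 20% for a subject's average score instead, 0.80 + 1.645 × 0.20/√n gives 85.0% at 43 and 84.0% at 68, close to the lower ends.

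**Step 5. Is the trial too small?** For an exact one-sample test against 50% (two-sided 0.05, one reading per subject), 29 of 43 or 43 of 68 correct would be needed. At a true rate of 80% the power is 98.4% and above 99.9% respectively. The low chance in Step 2 comes from where the threshold sits and not from a shortage of subjects.

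**Step 6. Photographs and satisfaction together.** With both true rates at 80% and one response per subject, each criterion has about a 50% chance. If the two are independent, the joint chance is 0.50 × 0.50 = 25%. With positive dependence it rises, to at most about 50%. The documents do not say how the two relate.

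**The case against.** The strongest reply is that the error harms only the sponsor. If reviewers merely guess, the chance of an observed 80% is about 0.00002 with 43 subjects and 0.0000001 with 68 (one reading per subject), so the rule is very unlikely to pass a device with no effect, and the sample is ample for showing better-than-chance identification. That is correct, and it limits the consequence: the fault lies in the power claim, and the rule does not invite a false claim of efficacy. It does not make the 95% figure true.

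A second reply is that 80% is called an objective, not a forecast, and that a device achieving 84–87% would pass with 95% probability. But 2.15.2 enters 80% as a mean with an SD, derives 43 from it and describes its inputs as assumptions. No higher expected rate appears anywhere, so 80% is the only planning value a reader can use.

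A third is that one binary reading per subject implies an SD of 40% (√(0.8 × 0.2)), against the plan's 20%. This moves the true rate needed for 95%, as Step 4 shows, but not the chance of about one half at a true rate of 80%.

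Two qualifications stand. This is a mismatch between the powered test and the decision rule; the 43 itself is calculated correctly. And the 25% joint figure is the independence end of a range from 25% to about 50%.

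**Conclusion.** The concern holds. The stated 95% power is not a property of the primary decision or of the satisfaction decision. At the planning rate of 80%, the chance of meeting the overall photograph rule is about 50% with 43 or 68 subjects (48–58% across the sample sizes and reviewer models tabulated), and 12.5% to 50% if 2.15.5 requires all three reviewers to pass. The claim that 43 patients secure a successful primary outcome is therefore wrong, and raising enrolment to 68 does not repair it.

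The conclusion rests on 80% being the planning value, on independent subjects with a common rate, and, for the reviewer-level and joint figures, on the stated ranges of dependence. It must be corrected, because the protocol misstates the chance of success for a criterion that the study has to meet.

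**What to change.** **Minimum change, sufficient on its own.** In 2.15.2, delete the 95% power claim for the photograph and satisfaction criteria. State that at a true rate of 80% the chance of meeting each 80% threshold is about 50%, and that a 95% chance on the photographs needs a true rate of about 84–87% with 68 evaluable subjects (about 87% for satisfaction, which has one response per subject). Say in 2.15.1 and 2.15.5 whether the photograph rule applies to the pooled rate or to every reviewer; if to every reviewer, quote the 12.5–50% range.

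**Optional alternative.** Make the rule match the calculation: declare photograph success if the lower limit of a two-sided 95% confidence interval for the correct rate, clustered by subject over the three reviewers, exceeds the 50% used in 2.15.2, and keep 80% as a descriptive target. This is a substantive choice. With 68 subjects and one reading each, 43/68 = 63% correct would pass, well below the present bar. It should be settled before any photographs are graded.

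**Cost.** Text in 2.15.1, 2.15.2 and 2.15.5, and the written IRB approval that section 21.0 requires for any protocol revision. No more patients are needed. The price is a less favourable stated chance of success or, under the alternative, a lower formal bar that would have to be defended.

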2.13 Evaluation Methods

Photographs:

Photographs will be taken prior to treatment 1, prior to treatment 4 (post treatment 3), and at all follow-up visits and may be taken at each treatment and will be used to assess safety and efficacy of treatment.

Blinded Evaluation:

Three blinded independent reviewers will perform a photographic evaluation in which they will be asked to identify pre-treatment images when compared to post treatment images. The reviewers will be Board Certified Dermatologists and be chosen based on availability and have relevant clinical experience. They will attend a training session prior to grading.

Caliper:

Caliper measurements on both flanks will be taken prior to treatment 1, prior to treatment 4 (post treatment 3), and at all follow-up visits and may be taken at each treatment.

Caliper Procedure:

The caliper device is a hand-held instrument like a compass, that is used to measure the distance between two opposite sides. The clinician will measure the flank by using a diagonal fold directly above the iliac crest. The patient's skinfold will be pinched approximately 1 cm from the measurement spot and the caliper will be placed on the skinfold. The caliper provides a measurement (millimeters) of the thickness of skin and fatty tissue. Three readings should be taken and an average of all three sites should be calculated and documented.

Treatment Discomfort/Pain Evaluation:

Subjects will be asked to report the general level of treatment discomfort on a scale of 0 (none) to 10 (maximum intolerable pain) using the universal pain assessment tool (Appendix B)

Subject Questionnaire:

The subject will be asked their level of satisfaction using a 6-point Likert scale that ranges from "extremely satisfied" to "extremely unsatisfied."

Subject Satisfaction	
Rating	Description
6	Extremely Satisfied
5	Satisfied
4	Slightly Satisfied
3	Slightly Unsatisfied
2	Dissatisfied
1	Extremely Unsatisfied

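### The 43-patient requirement in section 2.15.2 pairs two standard deviations on different bases, so no stated basis supports it (61 for a single reading; 21 to 61 for a three-reviewer mean)

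*Combined protocol and SAP*

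**What the plan says.** Section 2.15.2 specifies a two-sample t-test, two-sided 0.05, 95% power. It compares a hypothetical control at 50% correct with an objective of 80% correct.

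- Control SD: "with a standard deviation of 50% resulting from an equal amount of correct and incorrect answers".
- SD at the objective: "Our objective of 80% correct average evaluation of post treatment photos with a conservative 20% expected standard deviation". No source or derivation follows.
- Result: at least 43 patients. This is then adopted for the whole study as the largest figure over all outcomes.
- Satisfaction: "The sample size is calculated similarly to the primary outcome and yields the same results".
- Enrolment: "To allow for minor departures in these assumptions and to account of potential subject dropout it was decided to enroll 68 subjects". No dropout rate is given.

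Three other sections bear on the unit of analysis. Section 2.13 states "Three blinded independent reviewers will perform a photographic evaluation". Section 2.15.1 sets the 80% criterion on "Correct identification of pre-treatment images when compared to post treatment (12 week) images", without saying whether that is per reviewer or pooled. Section 2.15.5 states "Correct identification percentages will be calculated for each individual reviewer as well as a summary for all three reviewers". None of them defines a per-subject score averaged over reviewers, and none gives an expected level of reviewer agreement.

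**The concern.** The control SD is explained by its origin: equal numbers of correct and incorrect answers. That is the SD of a single yes/no reading. At 80% correct, a single yes/no reading has an SD of 40%, yet the plan uses half of that. The word conservative points the wrong way, because a smaller SD reduces the sample size.

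An SD below 40% is possible if each subject's score is an average of several readings. The control score would then be an average too, and its SD could not stay at 50%. The calculation appears to take one SD from each basis.

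At stake is the number on which the study's size rests. All outcomes are said to be covered by 43, and the enrolment of 68 is justified as an allowance above it. If 43 has no consistent basis, neither the requirement nor the allowance means what the section implies.

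**Working it through.** **Inputs from 2.15.2.** Difference 0.80 − 0.50 = 0.30; two-sided alpha 0.05; power 0.95; SDs 0.50 and 0.20. Equal group sizes are assumed, because the plan gives no ratio. Three reviewers are from 2.13. The correlation between reviewers on the same subject is not given, so the range 0 to 1 is an assumption.

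**Step 1: reproduce 43.** The normal approximation is n = (SD1² + SD2²)(1.960 + 1.645)² / 0.30².

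- n = (0.25 + 0.04) × 12.995 / 0.09 = 41.9, so 42.
- The noncentral t with 2n − 2 degrees of freedom gives 94.6% power at n = 42 and 95.1% at n = 43.

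The plan's 43 is therefore reproduced, as the size of one group, by SDs of 50% and 20%.

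**Step 2: the rule behind the control SD.** SD = sqrt(p(1 − p)).

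- p = 0.5: sqrt(0.25) = 50%, as stated.
- p = 0.8: sqrt(0.16) = 40%, against the plan's 20%.

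**Step 3: single-reading basis, SDs 50% and 40%.**

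- Normal approximation: (0.25 + 0.16) × 12.995 / 0.09 = 59.2, so 60.
- Noncentral t: 94.9% power at 60 and 95.3% at 61, so n = 61.
- Power at 43: 85.9%. Power at 68: 97.0%.

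**Step 4: three-reviewer mean.** Assume equal accuracy for all reviewers and one common correlation rho. Both SDs are then multiplied by sqrt((1 + 2·rho)/3).

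| rho (assumed) | SD at 50% | SD at 80% | n for 95% power | Power at 43 |
|---|---|---|---|---|
| 0 | 28.9% | 23.1% | 21 | >99.9% |
| 0.25 | 35.4% | 28.3% | 31 | 99.0% |
| 0.5 | 40.8% | 32.7% | 41 | 96.1% |
| 0.75 | 45.6% | 36.5% | 51 | 91.4% |
| 1 | 50.0% | 40.0% | 61 | 85.9% |

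By the same calculation, 43 is enough up to rho of about 0.56 (95.1%) and falls just short at 0.57 (94.9%, n = 44). In no row are the SDs 50% and 20%.

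**Step 5: satisfaction.** Section 2.15.5 counts each subject once, as satisfied or not, against an 80% threshold, so nothing is averaged. If the photograph comparator of 50% is carried over, the SDs are 50% and 40% and n = 61, as in step 3.

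**Step 6: the allowance within 68.** Above 43 it is 68 − 43 = 25 subjects (25/68 = 37%). Above 61 it is 68 − 61 = 7 (7/68 = 10%). With assumed losses of 10%, 15% and 21%, the evaluable numbers are 61, 58 and 54, and single-reading power is 95.3%, 94.3% and 92.7%.

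**The case against.** **The arithmetic is right.** The stated inputs do give 43. This stands: the fault is an unsupported and inconsistent input, not a slip in calculation.

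**An averaged score is a natural reading.** The text speaks of an average evaluation and there are three reviewers, so an SD below 40% is plausible and 43 lies inside the 21 to 61 range. The first part stands, and it is why 61 is conditional on a single reading. It does not rescue 43, because averaging must shrink the control SD as well. If averaging cuts 40% to 20%, the variance falls by a factor of 0.04/0.16 = 0.25. The control SD then becomes 25%, and the same formula needs 16. Near rho 0.56 the number 43 happens to be adequate, but with SDs of about 42% and 34%.

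**The control is hypothetical.** The two-sample formula charges sampling error to a group that is never sampled, and 2.15.5 plans no two-sample test of photographs. Against a fixed 50%, 43 subjects are ample. This stands and motivates the alternative fix, but it does not justify the derivation as printed.

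**Satisfaction has no stated comparator and no test.** This stands in part. The 61 holds only if the 50% comparator is borrowed, as the words on similar calculation suggest. It shows that the claim of equal results fails on the plan's formula, not that satisfaction needs 61 subjects.

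**No consequence is shown.** A reader might infer that the trial is underpowered. The documents do not support that: 68 exceeds 61, and part of the excess is there for departures from assumptions. The plan also states no percentage allowance; the 37% and 10% are derived here.

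**Conclusion.** The point holds as a defect in the sample-size rationale. The figure of 43 rests on one SD for a single reading and another, unsourced, that is half of what the same rule gives. On one consistent basis the plan's formula needs 61 (single reading; about 86% power at 43) or between 21 and 61 (three-reviewer mean). The second range assumes equal reviewer accuracy and a common correlation from 0 to 1. Because the plan does not state the unit, 43 cannot be called simply too low; it may be too many or too few.

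The satisfaction statement is wrong on the plan's formula if the 50% comparator is kept.

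The practical effect is limited. At 68 evaluable subjects, power is 97% on the single-reading basis, the least favourable of those considered. What changes is the stated requirement and, on that basis, the margin: 7 subjects above 61 rather than 25 above 43. How much of that margin dropout would use cannot be judged, because no rate is stated. The correction should be made, but enrolment need not change on this ground.

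**What to change.** In 2.15.2:

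1. State the unit of analysis: one reading per subject, or the mean of three reviewers with an assumed correlation and the reason for it.
2. Derive both SDs from p(1 − p) on that unit, and delete the word conservative.
3. Restate the required number. On the single-reading basis it is 61, with about 86% power at 43. Restate the allowance within 68 from the chosen figure, with an assumed dropout rate.
4. Replace the satisfaction sentence with the precision of the estimate: at 80% with 68 subjects, the 95% interval is about ±1.96 × sqrt(0.16/68) = ±9.5 points.

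Alternatively, because the control is hypothetical, size on an exact one-sample binomial test against 50% (upper tail at most 0.025, true rate 80%, single reading). With 35 evaluable subjects the critical count is 24 and power is 96.6%; with 43 it is 29 and 98.4%. The same test must then be added to 2.15.5, so that the study is not again sized on an analysis it does not plan. It should be labelled as power to beat chance, not as the probability of meeting the 80% success rule.

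The cost is a rewrite of 2.15.2, plus a sentence in 2.15.5 under the alternative, and the written IRB approval that section 21.0 requires for any revision. Enrolment, visits and data collection stay as they are.
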